4.6 Other secondary outcomes

Any p-values presented will be for descriptive purposes only, and should not be considered as formal statistical significance testing.

1. Coronary Heart Disease (CHD) death or subsequent non-fatal MI (type 1 or 4b);

This will be measured as the time from randomisation to the first relevant event. Patients discontinuing the study (for any reason) prior to reaching the outcome will have their time to outcome censored at the last contact date. Patients who die from a cause that is not part of the outcome, before achieving the outcome, will have their time to outcome censored at the date of death.

The analysis will use adjudicated outcome data, where these are available and relevant.

If the proportional hazards assumption holds, using visual inspection, then the relationship between intervention and this outcome will be analysed using Cox proportional hazard regression. The results will be expressed as a hazard ratio with the corresponding 95% confidence intervals and p-value. The primary analysis will be adjusted as specified in the Overall Statistical Principles section of this document. An unadjusted analysis will also be presented, as a sensitivity analysis.

The number of patients with an outcome event (by treatment group) will be tabulated, and the following statistics will be presented: adjusted HR (and 95% CI, p value), unadjusted HR (and 95% CI, p value). A Kaplan-Meier plot will be produced, showing results by allocated treatment.

2. Subsequent Non-fatal MI (type 1 or 4b);

This will be measured as the time from randomisation to the first relevant event. Patients discontinuing the study (for any reason) prior to reaching the outcome will have their time to outcome censored at the last contact date. Patients who die from a cause that is not part of the outcome, before achieving the outcome, will have their time to outcome censored at the date of death.

The analysis will use adjudicated outcome data, where these are available and relevant.

If the proportional hazards assumption holds, using visual inspection, then the relationship between intervention and this outcome will be analysed using Cox proportional hazard regression. The results

will be expressed as a hazard ratio with the corresponding 95% confidence intervals and p-value. The primary analysis will be adjusted as specified in the Overall Statistical Principles section of this document. An unadjusted analysis will also be presented, as a sensitivity analysis.

The number of patients with an outcome event (by treatment group) will be tabulated, and the following statistics will be presented: adjusted HR (and 95% CI, p value), unadjusted HR (and 95% CI, p value). A Kaplan-Meier plot will be produced, showing results by allocated treatment.

3. Non-cardiovascular death;

This will be measured as the time from randomisation to the first relevant event. Patients discontinuing the study (for any reason) prior to reaching the outcome will have their time to outcome censored at the last contact date. Patients who die from a cause that is not part of the outcome, before achieving the outcome, will have their time to outcome censored at the date of death.

If the proportional hazards assumption holds, using visual inspection, then the relationship between intervention and this outcome will be analysed using Cox proportional hazard regression. The results will be expressed as a hazard ratio with the corresponding 95% confidence intervals and p-value. The primary analysis will be adjusted as specified in the Overall Statistical Principles section of this document. An unadjusted analysis will also be presented, as a sensitivity analysis.

The number of patients with an outcome event (by treatment group) will be tabulated, and the following statistics will be presented: adjusted HR (and 95% CI, p value), unadjusted HR (and 95% CI, p value). A Kaplan-Meier plot will be produced, showing results by allocated treatment.

4. Invasive coronary angiography;

This will be measured as the time from randomisation to the first relevant event. Patients discontinuing the study (for any reason) prior to reaching the outcome will have their time to outcome censored at the last contact date. Patients who die before achieving the outcome, will have their time to outcome censored at the date of death.

If the proportional hazards assumption holds, using visual inspection, then the relationship between intervention and this outcome will be analysed using Cox proportional hazard regression. The results will be expressed as a hazard ratio with the corresponding 95% confidence intervals and p-value. The primary analysis will be adjusted as specified in the Overall Statistical Principles section of this document. An unadjusted analysis will also be presented, as a sensitivity analysis.

The number of patients with an outcome event (by treatment group) will be tabulated, and the following statistics will be presented: adjusted HR (and 95% CI, p value), unadjusted HR (and 95% CI, p value). A Kaplan-Meier plot will be produced, showing results by allocated treatment.

5. Coronary revascularisation;

This will be measured as the time from randomisation to the first relevant event. Patients discontinuing the study (for any reason) prior to reaching the outcome will have their time to outcome censored at the last contact date. Patients who die before achieving the outcome, will have their time to outcome censored at the date of death.

If the proportional hazards assumption holds, using visual inspection, then the relationship between intervention and this outcome will be analysed using Cox proportional hazard regression. The results will be expressed as a hazard ratio with the corresponding 95% confidence intervals and p-value. The

primary analysis will be adjusted as specified in the Overall Statistical Principles section of this document. An unadjusted analysis will also be presented, as a sensitivity analysis.

The number of patients with an outcome event (by treatment group) will be tabulated, and the following statistics will be presented: adjusted HR (and 95% CI, p value), unadjusted HR (and 95% CI, p value). A Kaplan-Meier plot will be produced, showing results by allocated treatment.

6. Percutaneous coronary intervention;

This will be measured as the time from randomisation to the first relevant event. Patients discontinuing the study (for any reason) prior to reaching the outcome will have their time to outcome censored at the last contact date. Patients who die before achieving the outcome, will have their time to outcome censored at the date of death.

If the proportional hazards assumption holds, using visual inspection, then the relationship between intervention and this outcome will be analysed using Cox proportional hazard regression. The results will be expressed as a hazard ratio with the corresponding 95% confidence intervals and p-value. The primary analysis will be adjusted as specified in the Overall Statistical Principles section of this document. An unadjusted analysis will also be presented, as a sensitivity analysis.

The number of patients with an outcome event (by treatment group) will be tabulated, and the following statistics will be presented: adjusted HR (and 95% CI, p value), unadjusted HR (and 95% CI, p value). A Kaplan-Meier plot will be produced, showing results by allocated treatment.

7. Coronary artery bypass graft;

This will be measured as the time from randomisation to the first relevant event. Patients discontinuing the study (for any reason) prior to reaching the outcome will have their time to outcome censored at the last contact date. Patients who die before achieving the outcome, will have their time to outcome censored at the date of death.

If the proportional hazards assumption holds, using visual inspection, then the relationship between intervention and this outcome will be analysed using Cox proportional hazard regression. The results will be expressed as a hazard ratio with the corresponding 95% confidence intervals and p-value. The primary analysis will be adjusted as specified in the Overall Statistical Principles section of this document. An unadjusted analysis will also be presented, as a sensitivity analysis.

The number of patients with an outcome event (by treatment group) will be tabulated, and the following statistics will be presented: adjusted HR (and 95% CI, p value), unadjusted HR (and 95% CI, p value). A Kaplan-Meier plot will be produced, showing results by allocated treatment.

8. Proportion of patients prescribed ACS therapies during index hospitalisation;

Table: N (%), odds ratio with 95% confidence interval, of patients prescribed ACS therapies during index hospitalisation; using logistic regression adjusted as specified earlier, with unadjusted analysis also presented.

Note: ACS therapy includes TNK/TPA, LMWH, tirofiban or equivalent 2B3A inhibitors, intravenous nitrate, aspirin, clopidogrel, prasugrel, ticagrelor.

9. Proportion of patients discharged on preventative treatment or have alteration in dosage of preventative treatment during index hospitalisation;

Statistical Analysis Plan	RAPID-CTCA
Version No	2.0
Date Finalised	19 Aug 2020

Table: N (%), odds ratio with 95% confidence interval; using logistic regression adjusted as specified earlier, with unadjusted analysis also presented.

Primary or secondary prevention treatment includes beta blocker, calcium channel blocker, ACE inhibitor or ARB, nicorandil, oral nitrate, buccal or sublingual nitrate, oral hypoglycaemic, insulin, statin, aspirin, clopidogrel, prasugrel, ticagrelor.

10. Length of stay for index hospitalisation;

This will be reported in Hours

Table: Descriptive statistics [continuous data].

Table: Difference between the intervention groups with 95% confidence interval, using Hodges Lehmann estimator of location shift, with a Moses distribution free confidence interval based on the Wilcoxon Rank Sum test.

11. Representation or rehospitalisation with suspected ACS/recurrent chest pain within 12 months [NB this is being interpreted as time from randomisation, not time from index hospitalisation]

This will be measured as the time from randomisation to the first relevant event. Patients discontinuing the study (for any reason) prior to reaching the outcome will have their time to outcome censored at the last contact date. Patients who die before achieving the outcome, will have their time to outcome censored at the date of death.

If the proportional hazards assumption holds, using visual inspection, then the relationship between intervention and this outcome will be analysed using Cox proportional hazard regression. The results will be expressed as a hazard ratio with the corresponding 95% confidence intervals and p-value. The primary analysis will be adjusted as specified in the Overall Statistical Principles section of this document. An unadjusted analysis will also be presented, as a sensitivity analysis.

The number of patients with an outcome event (by treatment group) will be tabulated, and the following statistics will be presented: adjusted HR (and 95% CI, p value), unadjusted HR (and 95% CI, p value). A Kaplan-Meier plot will be produced, showing results by allocated treatment.

12. Chest pain symptoms up to 12 months;

Table: N (%) of patients with 'No chest pain', 'Non-exertional chest pain', 'Chest pain on exertion' will be presented at month 1, 6, and 12 and summarised by allocated intervention group. No formal statistical testing will be performed.

13. Patient satisfaction at 1 month;

Data to be tabulated, without formal statistical testing.

14. Clinician certainty of presenting diagnosis after CTCA;

Table [continuous]: Present data on change from baseline, in addition to final values.

Note: clinician certainty of presenting diagnosis is on a scale of 0-10 where 0 is least certain and 10 is most certain

15. Quality of Life (measured by EQ-5D-5L up to 12 months).

NB Analysis of this outcome will be done by the health economics team, not the statistical team, and details are in the Health Economic Analysis Plan.

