Computerised Tomography coronary angiography (CTCA) involves using a CT scan to identify blockages in the coronary arteries. It is slightly less accurate at identifying obstruction than invasive coronary angiography but has much fewer risks. It could therefore be used to improve the investigation of medium-risk patients. It could be used to identify patients with significant blockage who require invasive coronary angiography, allowing treatment of the obstruction and reducing the risk of serious heart problems. It could also identify patients without significant obstruction who don't have a blockage and could therefore be discharged home, avoiding unnecessary tests and medication. However, although the ability of CTCA to detect obstruction is well known, it is unclear whether using CTCA leads to more appropriate use of coronary angiography and medication, a reduced risk of serious heart problems and improved patient outcomes.

The aim is to undertake a research study of CTCA in patients admitted to hospital with suspected or confirmed ACS in the group of patients who are at medium risk, excluding high-risk patients needing immediate coronary angiography and very low-risk patients who can be discharged home without further investigation.

Patients who are suitable will be given information about the study and asked to sign a consent form. Patients will be allocated to either receive CTCA as part of their assessment or receive standard assessment without this test. We will then follow up patients for one year to determine the rate of bad outcomes (such as heart attack or death), quality of life, patient satisfaction, the use of diagnostic tests or treatments, and health care costs. The study will be undertaken by an experienced team of UK researchers involved in previous successful trials in patients with chest pain. The team includes experts in emergency medicine, cardiology, radiology, acute medicine, statistics, and economics.

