This research is likely to have a significant impact on this large and important group of patients presenting with suspected or confirmed ACS to NHS hospitals. If the trial is positive, those patients with CAD will receive an early and accurate anatomical characterisation of coronary arteries by CTCA allowing targeting of ICA to those patients that are most likely to require revascularisation and facilitating early optimisation of primary and secondary preventive medicines. These interventions will save lives and reduce the burden of undiagnosed ischaemic heart disease. In patients with non-obstructive CAD or normal coronary arteries, it is likely to facilitate earlier discharge and prevent unnecessary ICA with the attendant risks. In terms of NHS benefit, this research is likely to lead to more optimal use of scarce expensive resources, reduced duration of hospital stay at the time of index presentation, and subsequent reduced hospitalisation. The early effective use of primary and secondary prevention will lead to lower long-term cardiovascular events.

If the trial is negative, the results will prevent widespread NHS adoption of an ineffective technology that, if implemented unnecessarily without significant patient outcome benefit, would substantially increase NHS costs and expose patients to unnecessary investigation with radiation exposure and potential anxiety related to a false positive diagnosis.

Additionally, the increasing use of high sensitivity troponin will result in many more patients who have elevated troponin measurements; some of these patients will not have ACS. CTCA will enable local screening of these patients and only select patients for ICA that will directly benefit from this intervention.

To reiterate, it is imperative that CTCA is proven to improve clinical and cost outcomes before widespread adoption in the NHS. A positive or indeed a negative trial is equally important and valuable to the NHS.

Evidence explaining why this research is needed now

HTA evidence synthesis

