2.1.2 Secondary Objectives

1. The proportion of patients receiving coronary angiography and revascularisation at index hospitalisation and during 12-month follow up.
2. The proportion of patients representing or readmitted to hospital with suspected ACS/recurrent chest pain up to one year after index presentation.
3. The use of cardiovascular treatment during index hospitalisation and preventative therapies on discharge.
4. Length of stay at index hospitalisation.
5. The use of NHS resource including hospitalisation and other investigations and interventions.
6. The proportion of patients with symptoms, morbidity and mortality up to one year.
7. Quality of life.
8. The incremental cost per QALY gained by providing CTCA compared to current standard practice.

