In general, analyses will be adjusted for study site (used to stratify the randomisation), baseline GRACE score (continuous), and previous CAD (yes/no), unless otherwise specified. Of note, study site will be included as a random effect (as there will be a large number of sites); whilst GRACE score, and previous CAD will be included as fixed effects. GRACE score will be adjusted for using a restricted cubic spline with 3 knots (thus using 2 degrees of freedom). The knots will be placed at the following percentiles of the predictor's marginal distribution: 0.1, 0.5, 0.9. Age is contained within GRACE score and will therefore not be adjusted for separately. Baseline GRACE score will be calculated from individual components, using the formula for predicting death or non-fatal MI within 6 months of admission with ACS [2], rather than using the GRACE score field in the database.

All analyses and data manipulations will be carried out using the most up to date version of SAS available [1].

4. List of Analyses

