Routine admission blood tests: Urea (mmol/L) [continuous], Creatinine (μmol/L) [continuous], Estimated glomerular filtration rate (ml/minute/1.73m²) [categorised], Alanine aminotransferase (Units/L) [continuous], Haemoglobin (g/L) [continuous], White blood cell count (x10⁹/L) [continuous], Random blood glucose (mmol/L) [continuous], Cholesterol (mmol/L) [continuous].

Observations within 60 minutes prior to randomisation: Respiratory rate (breaths per minute) [continuous], Oxygen saturation (SpO₂ %) [categorical], Fraction inspired oxygen (%) [categorical], Heart rate (beats per minute) [continuous], Systolic blood pressure (mmHg) [continuous], Diastolic

Statistical Analysis Plan	RAPID-CTCA
Version No	2.0
Date Finalised	19 Aug 2020

blood pressure (mmHg) [continuous], Capillary blood glucose (mmol/L) [continuous], Temperature (°C) [continuous].

Treating clinical impression at time of randomisation: ACS [categorical], Diagnosis [categorical], Diagnosis certainty ((0-10 where 0 is the least certain and 10 is the most certain) [continuous]

Concomitant medication: Beta blocker, Calcium channel blocker, ACE Inhibitor or ARB, Nicorandil, Oral nitrate, Buccal or sublingual nitrate, Oral hypoglycaemic, Insulin, Statin, Aspirin, Clopidogrel, Prasugrel, Ticagrelor, TNK/TPA, LMWH, Tirofiban or equivalent 2B3A inhibitors, Intravenous nitrate (including infusion), Fondaparinux, Unfractionated heparin, Bivalirudin, Novel anticoagulants, Intravenous morphine/opiate, Diuretic, Proton Pump Inhibitor, Ivabradine, Warfarin, Ranolazine.

Table: N (%) with any of medications listed prescribed before admission [Y/N] and N (%) for each medication, by treatment arm, and overall.

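### SAP 4.6 items 8 and 9 do not say whether continued or pre-randomisation drugs count, and they ignore recorded pre-admission use, so their odds ratios may say little about whether CTCA changed treatment

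*SAP*

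**What the plan says.** SAP 4.6 item 9 is the "Proportion of patients discharged on preventative treatment or have alteration in dosage of preventative treatment during index hospitalisation". Its list has 13 drugs or classes, among them statins, aspirin, beta blockers, insulin and oral hypoglycaemics. Item 8 is the proportion prescribed ACS therapies in the index stay, where "ACS therapy includes TNK/TPA, LMWH, tirofiban or equivalent 2B3A inhibitors, intravenous nitrate, aspirin, clopidogrel, prasugrel, ticagrelor". Aspirin, clopidogrel, prasugrel and ticagrelor are on both lists.

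Each item yields one N (%) and one odds ratio from logistic regression, adjusted and unadjusted. For the adjusted models, SAP section 3 says that "analyses will be adjusted for study site (used to stratify the randomisation), baseline GRACE score (continuous), and previous CAD (yes/no"), with site as a random effect. Pre-admission medication is not a covariate, although SAP 4.2 plans a table of "N (%) with any of medications listed prescribed before admission [Y/N"] and of each drug, by arm. All 13 item 9 entries and all 8 item 8 agents are in that 27-item list.

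The matching protocol objective (2.1.2) is "The use of cardiovascular treatment during index hospitalisation and preventative therapies on discharge". On the status of these outcomes, SAP 4.6 says: "Any p-values presented will be for descriptive purposes only".

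**The concern.** Neither item says whether a drug taken before admission and simply carried on makes the patient an event. Taken at face value, item 9 includes such drugs, yet its dose-alteration limb suggests that change may have been the interest. Two programmers could code different outcomes from this text.

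Item 8 has a second gap. Protocol 5.4.1 allows randomisation up to 24 hours after arrival, and drugs given before it cannot be effects of CTCA. Item 9 has one of its own: it does not say whether a stopped drug or a reduced dose is an alteration.

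History of ischaemic heart disease is one of the three entry routes (Protocol 4.2), so some participants will already be on listed drugs. If continued drugs count and prior use is common, most patients in both arms are events whatever CTCA does. A class added or stopped in someone who stays on another listed drug is then not registered.

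This matters because changed treatment is part of the trial's rationale. Protocol 1.1 expects CTCA to help by "facilitating early optimisation of primary and secondary preventive medicines", and the Lay Summary also mentions "avoiding unnecessary tests and medication" in patients without significant obstruction. If the primary result is neutral, readers will ask whether treatment changed at all. No table in the protocol or SAP crosses pre-admission drugs with in-hospital or discharge drugs; SAP 4.8 adds investigations, disposition and discharge diagnosis only.

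**Working it through.** The plan states no figure for items 8 and 9, so there is none to reproduce. The documents give no rates of prior use, starting or stopping; **every rate below is assumed**, to show the direction and rough size only.

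**1. Item 9 if continued drugs count.** Let u be the share of patients on at least one listed class before admission, t the share of those discharged on none of the 13 classes, and s the share of the others who start one. Then

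P(event) = u(1 − t) + (1 − u)s.

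Take s = 50% (control) and 60% (CTCA), so the odds ratio for starting is (0.60/0.40)/(0.50/0.50) = 1.50. Take t = 3% in both arms.

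| u | Control | CTCA | Points from continuers, each arm: u(1 − t) | Composite OR |
|---|---|---|---|---|
| 50% | 73.5% | 78.5% | 48.5 | 1.32 |
| 60% | 78.2% | 82.2% | 58.2 | 1.29 |
| 70% | 82.9% | 85.9% | 67.9 | 1.26 |
| 80% | 87.6% | 89.6% | 77.6 | 1.22 |

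For example, at u = 80% the control rate is 0.8 × 0.97 + 0.2 × 0.5 = 0.876 and the CTCA rate is 0.8 × 0.97 + 0.2 × 0.6 = 0.896. The odds ratio is (0.896/0.104)/(0.876/0.124) = 1.22. Of the 87.6 points in the control arm, 77.6 come from patients who stayed on a listed drug.

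**2. Item 8 if drugs given before randomisation count.** Let q be the share of both arms given a listed drug before randomisation, and p the share of the rest prescribed one afterwards: 30% (control) and 40% (CTCA), an odds ratio of 1.56. Then P(event) = q + (1 − q)p.

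| q | Control | CTCA | OR |
|---|---|---|---|
| 30% | 51% | 58% | 1.33 |
| 50% | 65% | 70% | 1.26 |
| 70% | 79% | 82% | 1.21 |

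**3. What the missing covariate costs.** I fitted logistic models to expected cell counts under the item 9 rates in step 1, with N = 1720 (Protocol 4.1), 1:1 allocation, previous CAD in 40% and an odds ratio of 6 between prior use and previous CAD. Site and GRACE score were not modelled.

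| u | OR (z), adjusted for CAD | OR (z), CAD and prior use |
|---|---|---|
| 50% | 1.33 (2.47) | 1.44 (2.78) |
| 80% | 1.23 (1.32) | 1.32 (1.54) |

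The second odds ratio is a different quantity, conditional on prior use. The larger z shows that the covariate adds information which previous CAD does not carry.

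**4. Whether a new-start row could replace the composite.** Suppose CTCA acts only in non-users, and 30% of prior users in both arms add a class. The any-class new-start rates are 0.3u + (1 − u)s. At u = 50% they are 40% vs 45% (OR 1.23), and at u = 80% they are 34% vs 36% (OR 1.09). Both odds ratios are below the composite's 1.32 and 1.22. The new row should therefore stand beside the composite.

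**The case against.** The strongest reply is that the protocol objective concerns use of treatment, not change in it. Prior use is fixed before randomisation, so the comparison of arms is unbiased for use. A composite odds ratio nearer to 1 than the new-start odds ratio is a different quantity and not an error. The p-values are descriptive, and neither the primary outcome nor the testing hierarchy is touched. All of this stands, and it keeps the point minor.

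A reader might go further and infer that starts and stops would cancel or reverse the odds ratio. The formula in step 1 can produce this: the odds ratio is 1.00 if t in the CTCA arm is 13.0, 9.7, 7.3 or 5.5% at 50, 60, 70 or 80% prior use, with control still at 3%. The documents do not support that reading:

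- Here t means leaving on none of the 13 classes. Nothing suggests that CTCA would take that many prior users off every listed drug. The Protocol Appendix 1 table recommends preventative therapy, or says to consider it, at every level of disease, and no row mentions stopping a drug.
- It ignores the dose-alteration limb. If stopping counts as an alteration, stoppers are events and P = u + (1 − u)s. The odds ratio is then 1.33 at 50% prior use (75% vs 80%) and 1.28 at 80% (90% vs 92%), whatever the stop rates.

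Other objections also hold in part:

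- The Lay Summary's avoided medication may mean drugs not started, so the proposed new-start row can hide opposite effects too. With starts going from 50% to 70% in half of the non-users and from 50% to 30% in the other half, its odds ratio is 1.00.
- If nearly all prior users have the outcome, the prior-use covariate almost separates the data and the fit may fail.
- Pre-admission use does not deal with drugs given between arrival and randomisation.
- The CRF and the Health Economics Analysis Plan are not among the documents. The first may define continued or altered status, and the economic analysis costs drug therapy per patient (Protocol 8).

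These points shape the fix. They do not remove the silence in items 8 and 9 or the omitted covariate.

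**Conclusion.** The point holds and is minor. Items 8 and 9 are valid descriptive comparisons of treatment use. As written, they leave open which drugs count, and their odds ratios may be close to saturated and so say little about whether CTCA changed treatment. The adjusted models also omit a recorded baseline value that should predict these outcomes strongly.

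The size cannot be determined from the documents. Under the assumed rates, a new-start odds ratio of 1.50 shows as 1.32 to 1.22 over 50 to 80% prior use, and adding prior use raises z from 2.47 to 2.78 (50%) or from 1.32 to 1.54 (80%). The item 9 dilution applies only if continued drugs count, and the illustrated figures assume equal stopping in both arms.

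It would go too far to call the composites wrong, or to say that starts and stops are likely to offset each other. The second claim needs stopping to mean discharge on none of the listed classes, and stopping not to be an alteration; the documents establish neither. The absence of a start/stop table is established for the protocol and SAP only.

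**What to change.** In SAP 4.6, items 8 and 9:

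1. Keep both composites and both unadjusted analyses. Add pre-admission use of at least one drug on the item's list (yes/no, from the SAP 4.2 data) as a fixed effect in the adjusted logistic models. Note that the odds ratio is then conditional on prior use. If nearly all prior users have the outcome, use a penalised (Firth-type) fit or drop the term.
2. Add descriptive rows by arm with N (%), odds ratio and 95% CI for (i) any listed class newly started relative to pre-admission use, with users of other listed drugs kept in the denominator, and (ii) among prior users, any listed class stopped.
3. State whether these count: drugs continued unchanged (both items), drugs given between arrival and randomisation (item 8), and stopped or reduced drugs as an alteration (item 9). Item 11 already has a note of this kind on how its time window is interpreted.

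The cost is some wording, one covariate and a few table rows. Parts 1 and 3 use pre-admission data that are already tabulated. Part 2 can be done only as far as the CRF records discharge drugs by class. Protocol section 7 lists regular treatment among the data collected but does not show this. The downside is a few more descriptive estimates and a new-start row that may be less sensitive than the composite. The wording is best settled before results by arm are seen.
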